## **Sex**

### 8. Male

Contraceptive use by men should be consistent with local regulations regarding the methods of contraception for those participating in clinical studies.

Male participants are eligible to participate if they agree to the following during the intervention period and for at least time required for 3 consecutive ejaculate samples to test negative for vector shedding:

- Refrain from donating sperm.

PLUS either:

- Be abstinent from heterosexual or homosexual intercourse as their preferred and usual lifestyle (abstinent on a long term and persistent basis) and agree to remain abstinent.

OR

- Must agree to use contraception/barrier as detailed below:

Agree to use male condom when engaging in any activity that allows for passage of ejaculate to another person

## **Informed Consent**

9. Capable of giving signed informed consent as described in Appendix 1 which includes compliance with the requirements and restrictions listed in the Informed Consent Form (ICF) and in this protocol

### **5.2. Exclusion Criteria**

Unless otherwise specified, participants who meet any of the following criteria at screening or prior to dosing of PF-06838435 (Day 0) are not eligible for the study. See [Section 8.10](#) for additional study assessments:

1. Hepatitis B screening (acute and chronic):

- A participant who has either Hepatitis B surface antigen (HBsAg) assessment which is positive, or HBV-DNA is positive/detectable.
- A participant who is currently undergoing anti-viral therapy for hepatitis B.

2. Hepatitis C screening (acute or chronic):

- A participant who is currently undergoing anti-viral therapy for chronic hepatitis C
- A participant is not eligible if his HCV-RNA load assay result is positive/detectable.

3. Significant underlying liver disease.

- A participant is not eligible if any of the following pre-existing diagnoses, which are indicative of significant underlying liver disease, are present in the medical record:
    - Portal hypertension, or;
    - Splenomegaly; or
    - Hepatic encephalopathy.
  - All participants who do not have the listed pre-existing diagnoses in (1) must have the following assessments performed at Screening:
    - A participant is not eligible if the serum albumin level is below the testing laboratory's lower limit of normal; and
    - At least one of the following diagnostic tests for liver fibrosis indicates  $\geq$  stage 3. The following results are indicative of fibrosis  $\geq$  stage 3 and exclude the participant from participation:
      - FibroScan, with a score  $>8.3$  kPa units
      - FibroTest/FibroSURE with a result  $>0.48$ ; or
      - AST-to-Platelet Ratio Index (APRI)  $>1$ .
4. Have serological evidence of HIV-1 or HIV-2 with CD4 counts  $\leq 200/\text{mm}^3$ . Participants who are HIV-positive and stable, have an adequate CD4 count ( $>200/\text{mm}^3$ ) and undetectable viral load ( $<50$  gc/mL) documented in prior medical records and at Screening, and are on an antiretroviral drug regimen are eligible to enroll;
5. Participants receiving  $5 \times 10^{11}$  vg/kg with anti-AAV-Spark100 neutralizing antibody titers  $\geq 1:5$ ; [REDACTED] CCI [REDACTED] [REDACTED] [REDACTED]
6. Have history of chronic infection or other chronic disease that the Investigators consider to constitute an unacceptable risk;
7. Have been dosed in a previous gene therapy research trial within the last 52 weeks or enrolled in a clinical study with an investigational drug within the last 12 weeks
8. Any concurrent clinically significant major disease, or other unspecified reasons that, in the opinion of the Investigator, and/or Sponsor makes the participant unsuitable for participation in the study; and
9. Unable or unwilling to comply with the schedule of visits and study assessments described in the clinical protocol.

### 5.4. Screen Failures

Screen failures are defined as participants who consent to participate in the clinical study but are not subsequently entered in the study. A minimal set of screen failure information is required to ensure transparent reporting of screen failure participants to meet the Consolidated Standards of Reporting Trials (CONSORT) publishing requirements and to respond to queries from regulatory authorities. Minimal information includes demography, screen failure details, eligibility criteria, and any SAE.

Individuals who do not meet the criteria for participation in this study (screen failure) may be rescreened in consultation and with the agreement of the medical monitor.

## 6. STUDY INTERVENTION

Study intervention is defined as any investigational intervention(s), marketed product(s), placebo, or medical device(s) intended to be administered to a study participant according to the study protocol.

### 6.1. Study Intervention(s) Administered

Refer to investigational product (IP) manual for specifics on the preparation, storage, handling, disposal, and accountability of investigational product.

ARM Name	PF-06838435/Fidanacogene elaparvovec
Intervention Name	PF-06838435/Fidanacogene elaparvovec
Type	Gene Therapy
Dosage Form	Injectable
Strength	1.00 x 10  vg/mL This is the nominal strength. The actual strength for each lot will be provided for dose calculation
Dosage	5x10  vg/kg single administration 1x10  vg/kg single administration 2x10  vg/kg single administration  For participants with body mass index (BMI) exceeding 30 kg/m  , the study dose will be calculated based on an adjusted body weight

	determination that assumes a maximum permissible BMI of 30 kg/m  . For example, a subject who is 6'2" and weighs 370 pounds (BMI 47.5 kg/m  ) would receive a vector dose based on an adjusted body weight of 234 pounds (which is the body weight associated with a BMI of 30 kg/m  for a 6'2" individual).
Route of Administration	Intravenous infusion/injection
IMP and NIMP	IMP (investigational medicinal product)
Sourcing	Provided centrally by the Pfizer
Packaging and Labeling	Study Intervention will be provided in a 2 mL vial Each vial will be labeled as required per country requirement.
Current/Former Names	PF-06838435, SPK-9001, AAV Spark100 hFIX39-Padua, Adeno associated viral vector with human factor IX Padua gene.

### 6.1.1. Dose Schedule and Administration

Refer to [Figure 1](#) for the Study Schematic and Study Specifics ([Section 4.1.1](#)) for a description of the sequence of enrollment. Following the bolus infusion of the participant's usual FIX protein product in about 10 minutes for FIX incremental recovery, the participant will be infused with PF-06838435 IV for approximately 60 minutes via infusion pump. The rate of administration should be determined based on the total volume of the PF-06838435 required for the participant to infuse for approximately 60 minutes.

### 6.1.2. FIX Incremental Recovery of FIX Products

Participants should be reminded to have washout of at least 96 hours (4 days) without FIX protein product, or longer washout for extended half-life FIX protein product, prior to any blood draw and infusion on Day 0. On Day 0 participants will be infused with 100 IU/kg of their usual FIX protein product over 10 (±2) minutes, under the supervision from the site staff and/or Investigator(s) to assess FIX incremental recovery. Number of vials, total volume, and total dosage are monitored and recorded by the site staff.

### 6.2. Preparation/Handling/Storage/Accountability

The investigational product must be stored in a secure location. Accountability for the study drug is the responsibility of the Investigator. More details concerning this responsibility are included in the IP Manual. The Investigator or his/her designee is responsible for the proper dispensing of the investigational product. The IP is to be dispensed only to participants who are enrolled and eligible based on the inclusion and exclusion criteria in this study. IP vials are for one time use only; any IP remaining in the vial after infusion should not be used for another subject.

Study site staff and investigational pharmacy personnel should refer to the Pharmacy Brochure for specific instructions on the handling, preparation, administration, and disposal of the investigational product.

1. The investigator or designee must confirm appropriate temperature conditions have been maintained during transit for all study intervention received and any discrepancies are reported and resolved before use of the study intervention.
2. Only participants enrolled in the study may receive study intervention and only authorized site staff may supply or administer study intervention. All study intervention must be stored in a secure, environmentally controlled, and monitored (manual or automated) area in accordance with the labeled storage conditions with access limited to the investigator and authorized site staff.
3. The investigator, institution, or the head of the medical institution (where applicable) is responsible for study intervention accountability, reconciliation, and record maintenance (ie, receipt, reconciliation, and final disposition records).
4. Further guidance and information for the final disposition of unused study interventions are provided in the IP Manual.

Ordering the IP and Preparation: Details are provided in the IP Manual and it should be reviewed carefully. Once eligibility has been confirmed, the IP can be ordered noting that will take at least 3 weeks for product delivery

### **6.3. Measures to Minimize Bias: Randomization and Blinding**

#### **6.3.1. Screening of Participants**

Participants must provide consent before any screening tests or assessments are performed. At the time of consent, the participant will be enrolled into the study. Participating study sites are required to document all screened candidates initially considered for inclusion in this study. If a participant is excluded from the study, the reasons for exclusion will be documented in the participant's source documents and on the screening log.

Participants may have screening laboratory results repeated once if the initial test falls outside of the protocol criteria. At the second screening, the participant will be assigned a different participant identification number.

For participants whose genotype is not known, a sample will be drawn for analysis at screening. This is not an inclusion or exclusion criterion; the participant's refusal to have this genotype sample taken would not exclude the participant from the study unless the severity of the disease is unable to be verified due to inadequate washout.

Genotyping may provide information regarding the predisposition of genotypic subpopulations to experience different bleeding frequencies. The development of an inhibitor to treatment with factor concentrates is the single most serious complication of factor replacement. One of the decisive risk factors for the development of inhibitors is the type of mutation (eg, deletion or missense) that codes for a protein that may be absent, truncated, or present, but not functional. There is a correlation between the resultant protein and the likelihood of developing inhibitors to factor replacement.

### **6.3.2. Enrollment of Participants**

Each participant will be assigned a unique participant identification number after the informed consent process is completed. No participant may be dosed prior to obtaining the unique participant identification number. The Investigator must confirm and verify the eligibility per criteria in [Section 5.1](#) and [Section 5.2](#) (following the review of screening results from the certified clinical laboratory and other documents). Participant identification numbers that are assigned will not be reused even if the participant does not receive investigational product or fails screening.

### **6.3.3. Randomization**

Not applicable. This is a non-randomized study.

### **6.3.4. Blinding Procedures**

Not applicable. This is an open-label study.

## **6.4. Study Intervention Compliance**

Deviation(s) from the prescribed dosage regimen should be recorded in the electronic case report form (eCRF).

Compliance with the infusion of FIX protein product and PF-06838435 on Day 0 is to be monitored and recorded by site staff.

After the infusion of FIX protein product on Day 0, participants will immediately be infused with PF-06838435. PF-06838435 will be infused via infusion pump and will be supervised by the investigational staff. The vial lot number, total volume, and infusion time are monitored and recorded by the site staff. Therefore, full compliance with PF-06838435 infusion is anticipated.

## **6.5. Concomitant Therapy**

The use of concomitant therapies or procedures, as defined below, must be recorded on the participant's eCRF, according to instructions for eCRF completion. AEs related to administration of these therapies or procedures must be documented on the appropriate eCRF.

A concomitant therapy is any drug or substance administered between participant consent (at Screening) and last study visit. Participants taking medication routinely for a pre-existing condition should be on a regimen, which has been stable for at least 3 weeks, and dosage changes should not be anticipated during the post-infusion period for this study. All concurrent prescription and non-prescription medications, including over-the-counter and alternative preparations (including herbal remedies, vitamins, and health food supplements), should be recorded at baseline and throughout the study period.

Medication use in the 30 days prior to screening, as well as the use of concomitant therapies or procedures must be recorded on the participant's eCRF, according to instructions for

eCRF completion. AEs related to administration of these therapies or procedures must be documented on the appropriate eCRF.

### 6.5.1. Allowed Therapy

During the study participants are requested to temporarily suspend their prophylaxis regimen, but participants may take:

- FIX product, as needed. Usage of clotting factors (product, date, dosage, reason) will be recorded in the infusion log.

Participant should be instructed to discuss any new medications, including non-prescription drugs and herbal preparations, with the Investigator prior to taking them.

Other therapies considered necessary for the participant's welfare may be given at the discretion of the Investigator. All such therapies must be recorded in the eCRF.

### 6.5.2. Disallowed Therapy

The following concomitant medications are not permitted during the study:

1. Blood products such as red blood cells (RBC), platelets, and fresh frozen plasma, except as required during a surgery.
2. Non-steroidal anti-inflammatory drugs that are known to inhibit platelet function, for example naproxen, aspirin, ibuprofen.
3. Acetylsalicylic acid (aspirin) or ibuprofen; however, other non-steroidal anti-inflammatory drugs are permitted.
4. Participants who are participating in other investigational therapies and concomitantly used with PF-06838435.
5. Any other therapies under investigation and concomitantly used with the investigational product (participants are not allowed to participate concurrently in another clinical study).

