5.2. Protocol Deviations

Protocol deviations/violations will be presented in a data listing.

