7.1. Prior and Concomitant Medications

Prior and Concomitant medications will be summarized separately by anatomical therapeutic chemical, medication names and dose group using the safety analysis set. Prior medications include all medications taken within 30 days prior to screening to the PF-06838435 infusion date.

Concomitant medications are any medication or substance that has a stop date that is on or after the date of PF-06838435 infusion.

Prior and concomitant medication will be coded using WHODRUG version June 1, 2015 (will be updated once per year).

Data on both prior and concomitant medications will be displayed in a data listing. Number of days from infusion of PF-06838435 to the start/stop date of prior or concomitant medication will be included.

Medications with start/stop dates that are partially missing will be analyzed in the summary tables as follows; Original dates will be displayed in the listings.

- If the start date is partially missing: a '01' will be used for the day and 'Jan' will be used for the month
- If the stop date is partially missing: a '28', '29', '30', or '31' will be used for the day (depends on the month and the year) and 'Dec' will be used for the month.

If the start date of a concomitant medication is completely missing, then the therapy will be included in the concomitant medications summary table if the stop date of the medication is on or after the date of PF-06838435 infusion.

An additional listing will be provided for the use of corticosteroids or alternative immunosuppressive therapy in any individual who develops hepatic transaminase elevation of 1.5-fold above baseline or successively increasing over baseline.

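### Protocol Section 6.5.2 both bans and permits naproxen: items 2 and 3 of the prohibited-medication list give different rules for NSAIDs

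*Protocol*

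**What the plan says.** Protocol Section 6.5.2 opens with "The following concomitant medications are not permitted during the study", so each numbered item below it should be a prohibition.

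- Item 2: "Non-steroidal anti-inflammatory drugs that are known to inhibit platelet function, for example naproxen, aspirin, ibuprofen".
- Item 3: "Acetylsalicylic acid (aspirin) or ibuprofen; however, other non-steroidal anti-inflammatory drugs are permitted".

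Three other places bear on the point:

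- Protocol Section 6.5 requires all medicines to be recorded and routine ones to be stable before entry. It says nothing about NSAIDs.
- Protocol Section 6.5.1 states that "During the study participants are requested to temporarily suspend their prophylaxis regimen". It asks them to speak to the investigator before starting any new medicine, over-the-counter products included, and adds that "Other therapies considered necessary for the participant's welfare may be given at the discretion of the Investigator". It does not mention NSAIDs either.
- In the SAP, Section 5.2 says "Protocol deviations/violations will be presented in a data listing". Section 7.1 provides a listing of prior and concomitant medications, for which "Number of days from infusion of PF-06838435 to the start/stop date of prior or concomitant medication will be included".

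**The concern.** Item 2 defines its ban by a property (platelet inhibition) and illustrates it with three drugs. Item 3 defines its ban by name (two drugs) and then permits the rest of the class without qualification. The two rules differ for every platelet-inhibiting NSAID other than aspirin and ibuprofen, and one such drug, naproxen, is named in item 2. An investigator asked whether a participant may take naproxen finds both answers in consecutive lines.

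The question is likely to come up. On-demand participants can qualify through chronic hemophilic arthropathy with joint pain (Protocol Section 5.1, criterion 4), and a pain questionnaire is scheduled (Schedule of Activities, note 21). Participants enter with endogenous factor IX of 2% or less and are asked to pause prophylaxis.

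Two things are at stake. The first is safety: a site relying on item 3 could allow a drug that item 2 treats as impairing platelets in people with a bleeding disorder. The second is consistency across centers: identical naproxen use could be a deviation at one site and acceptable at another, which would make the deviation listing uneven. Some added noise in the exploratory bleeding data is possible, but the documents give no basis for sizing it.

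**Working it through.** No alpha, power, effect size or sample size is involved, and the plan states no figure to reproduce. The check sets the two items side by side and then looks for text that would reconcile them.

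**Step 1. Apply each item as written.**

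| Drug | Item 2 | Item 3 | Result |
|---|---|---|---|
| Aspirin | banned (named) | banned (named) | consistent |
| Ibuprofen | banned (named) | banned (named) | consistent |
| Naproxen | banned (named) | permitted (an NSAID other than the two named) | contradiction |
| Any other platelet-inhibiting NSAID | banned (by property) | permitted | contradiction |
| An NSAID that does not inhibit platelets | not covered | permitted | consistent |

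No outside pharmacology is needed for naproxen, because item 2 itself classes it as a platelet-inhibiting NSAID.

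**Step 2. Count.** Item 2 names 3 drugs. Item 3 bans 2 of them. Named drugs in conflict: 3 − 2 = 1 (naproxen). Item 2's drugs are only examples, so the unnamed platelet-inhibiting NSAIDs in the fourth row are in conflict too. Their number cannot be taken from the documents.

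**Step 3. Duration.** The list applies for the whole study. Protocol Section 4.1.7 gives up to 6 weeks of screening plus 52 weeks of observation: 6 + 52 = 58 weeks per participant, approximately.

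**Step 4. Look for text that ranks the items.** Protocol Section 6.5 covers recording and stable regimens only. Section 6.5.1 covers consultation and general discretion only. SAP Sections 5.2 and 7.1 cover listings only. None of them refers to NSAIDs or says which item governs.

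**Step 5. Trace the effect on the analysis.** The readable analysis sets (Protocol Section 9.3, SAP Section 4.3) depend on consent, on dosing, and on having usable factor IX samples. None excludes a participant for a deviation. The secondary endpoints are factor IX activity and antigen, and dose escalation and expansion turn on factor IX activity, immune response and safety review. The NSAID wording enters none of these. It reaches only the classification of deviations in the SAP Section 5.2 listing and, through actual drug exposure, the bleeding rate that Protocol Section 8.1 treats as exploratory.

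**The case against.** The best reply is that the list is cumulative: a drug caught by any item is prohibited, and a ban that names naproxen outranks a general permission. On that reading, other in item 3 means NSAIDs outside both items, and the combined rule is coherent: platelet-inhibiting NSAIDs are banned and the rest are allowed. A cautious site may well read it so. But this reading has to be inferred. Within item 3, the only drugs that other can refer back to are aspirin and ibuprofen, and the item does not mention item 2. The reading also leaves item 3's ban with no work to do, since item 2 already names both drugs.

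Four further points carry some weight:

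- **The risk state is easy to overstate.** A factor IX level of 2% or less is the entry criterion. The pause in prophylaxis starts after vector infusion (Schedule of Activities, note 16), when vector-derived factor IX is expected, and factor IX product is available as needed. This stands. The exposure of concern is narrower than the full 58 weeks and lies mainly in the early weeks and in participants with low expression.
- **Consultation is a partial safeguard.** A clinician stands between the wording and the drug. That is true, but the clinician consulted must still apply Section 6.5.2.
- **The effect on the analysis is close to nil.** Deviations are only listed, and NSAID use is recorded whatever its label. Inconsistent labels change no readable summary statistic; any noise in bleeding data would come from the drug use itself. This stands.
- **One of three named drugs is a count of words.** It does not measure impact. This also stands.

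**Conclusion.** The contradiction is real: as written, Section 6.5.2 both prohibits and permits naproxen, along with every other platelet-inhibiting NSAID that item 3 does not name. It is a minor point. Its substance is the safety instruction to sites and the uniform labelling of deviations. It does not bear on the factor IX endpoints, dose decisions or analysis sets.

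The conclusion rests on the plain reading of item 3, in which other refers to the two drugs just named, and on the readable text of both documents. The documents give no rate of NSAID use, so no number of affected participants and no effect on bleeding rate is claimed.

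**What to change.** Delete item 3. Nothing is lost from the prohibition, because item 2 already names aspirin and ibuprofen, and NSAIDs without platelet effect remain outside the ban. If the sponsor wants the permission stated, reword item 3 to say only that NSAIDs which do not inhibit platelet function are permitted.

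Use that single rule to classify NSAID use as a deviation, or not, for the SAP Section 5.2 listing. If dosing is already complete, the rule can still be applied to the recorded concomitant medications.

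Optionally, bleeds that start during recorded use of a platelet-inhibiting NSAID could be flagged from the timing data in the SAP Section 7.1 listing. The correction does not depend on this.

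The cost is one line of protocol text and no new data collection. The optional flag would be derived from data already collected.
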